5.5.7. Profile of Mood States 2nd edition (POMS-2)

The POMS-2 is a self-report measure that allows for the quick assessment of transient, fluctuating feelings, and enduring affect states.^{4,5} Full-length versions (65 items) yield several scale scores: Anger-Hostility, Confusion-Bewilderment, Depression-Dejection, Fatigue-Inertia, Tension-Anxiety, Vigor-Activity and Friendliness. Each item is rated on a scale of 0 to 4 (0= “not at all”, 1= “a little”, 2= “moderately”, 3= “quite a bit”, 4= “extremely”). Total Mood Disturbance is a function of these 6 scale scores, shown in [Table 9](#). The recall period for this study is 7 days.

Table 9: POMS-2 Scoring

| Component | Questions |
|------------------------------|--|
| Anger-Hostility (AH) | Sum of 3, 14, 21, 28, 30, 35, 38, 43, 48, 49, 52 |
| Confusion-Bewilderment (CB) | Sum of 6, 8, 15, 25, 34, 46, 50, 54, 58, 63 |
| Depression-Dejection (DD) | Sum of 5, 11, 18, 20, 29, 32, 33, 40, 41, 44, 53, 56, 61 |
| Fatigue-Inertia (FI) | Sum of 4, 26, 36, 42, 45, 59 |
| Tension-Anxiety (TA) | Sum of 2, 9, 13, 17, 19, 23, 24, 31, 37, 65 |
| Vigor-Activity (VA) | Sum of 7, 12, 16, 47, 55, 57, 60, 62, 64 |
| Friendliness (F)* | Sum of 1, 10, 22, 27, 39, 51 |
| Total Mood Disturbance (TMD) | AH + CB + DD + FI + TA – VA |

*F does not contribute to TMD

Descriptive statistics (N, mean, median, minimum, and maximum) of the total scores and each component scores, as well as the changes from baseline will be summarized at each time point during PT phase and follow-up phases. Mean (SE) POMS-2 values, total scores and each component scores, will be presented graphically for PT phase and follow-up phases.

6. Pharmacokinetics/Pharmacodynamics Analysis

All plasma concentrations below quantification limit (BQL) or missing data will be labeled as such in the concentration data presentation. All subjects and samples excluded from the analysis will be clearly documented in the Clinical Study Report.

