The criteria of TRD is defined as nonresponse ($\leq 25\%$ improvement) to at least 1 antidepressant treatment determined retrospectively and 1 antidepressant prospectively in the current episode of depression. After 6 weeks, subjects who are nonresponders to the new oral antidepressant treatment at the end of the prospective lead-in phase can be eligible to proceed to the double-blind induction phase. Nonresponse at the end of the prospective lead-in phase is defined as $\leq 25\%$ improvement in the MADRS total score from Visits 2.1 to each of Visit 2.3 and 3.1 (prerandomization) respectively, and a MADRS total score of ≥ 28 on each of the Visits 2.1, 2.3, and 3.1 (prerandomization). Assessment of antidepressant treatment response at the end of the prospective lead-in phase will be performed by investigators. All other subjects who do not proceed to the double-blind induction phase will end study participation at this time. No follow-up or further study visits will be performed for these subjects. All subjects who are discontinued must be treated with an oral antidepressant after completion of the study, unless it is clinically inappropriate.

MADRS assessment throughout the study will be performed by an independent, remote, blinded rater.

Double-blind Induction Phase

The 4-week fixed dose double-blind induction phase will start on Day 1 (Visit 3.1) and end at Day 28 (Visit 3.10). A total of 183 subjects will be randomly assigned in a 2:1:1:1 ratio to receive double-blind intranasal treatment with either placebo, esketamine 28 mg, esketamine 56 mg, or esketamine 84 mg add-on to the continued stable oral antidepressant initiated in the prospective lead-in phase. The intranasal treatment sessions (esketamine or placebo) will occur twice weekly. Subjects will self-administer the intranasal study drug (esketamine 28 mg, 56 mg, 84 mg, or placebo) at treatment sessions occurring twice a week for 4 weeks at the clinical site under clinical supervision. The first treatment session will be on Day 1.

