On all intranasal treatment session days, subjects must remain at the clinical site until study procedures have been completed and the subject is ready for discharge.

MOAA/S

The MOAA/S will be used to measure treatment-emergent sedation with correlation to levels of sedation defined by the American Society of Anesthesiologists (ASA).⁵⁰

The MOAA/S scores range from 0 (no response to painful stimulus; corresponds to ASA continuum for general anesthesia) to 5 (readily responds to name spoken in normal tone [awake]; corresponds to ASA continuum for minimal sedation).

On each intranasal treatment session day, the MOAA/S will be performed every 15 minutes from pre-dose to 1.5 hours postdose.

- If the score is ≤ 3 at any time during the 1.5-hour postdose interval, the MOAA/S will be performed every 5 minutes until a score of 4 is reached (at which point a frequency of every 15 minutes can be resumed until 1.5-hour postdose).
- If a subject does not have a score of at least 5 at 1.5-hour postdose, he/she should continue to be monitored. For subjects with a score of 4, the assessment should be repeated every 15 minutes. And for subjects with a score of ≤ 3 , the assessment should be repeated every 5 minutes until the score returns to 5 or the subject is referred for appropriate medical care, if clinically indicated.

POMS-2

The POMS-2 will be used to measure the abuse-liability of intranasal esketamine administered twice a week for 4 weeks, at time points outlined in [TIME AND EVENTS SCHEDULE 1](#) and [TIME AND EVENTS SCHEDULE 2](#).

The POMS-2 is a self-report measure that allows for the quick assessment of transient, fluctuating feelings, and enduring affect states. Full-length versions (65 items) yield several scale scores: Anger-Hostility, Confusion- Bewilderment, Depression-Dejection, Fatigue-Inertia, Tension-Anxiety, and Vigor-Activity. Total Mood Disturbance is a function of these 6 scale scores. The recall period for this study is 7 days.

PWC-20

The PWC-20 will be administered to assess potential withdrawal symptoms following cessation of intranasal esketamine treatment at time points outlined in [TIME AND EVENTS SCHEDULE 1](#), [TIME AND EVENTS SCHEDULE 2](#), and [TIME AND EVENTS SCHEDULE 3](#).

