The ECG variables that will be analyzed are heart rate, PR interval, QRS interval, QT interval, and corrected QT (QTc) interval using the following correction methods: QT corrected according to Bazett's formula (QTcB) and QTcF.^{2,31,60}

Descriptive statistics of QTc intervals and changes from baseline will be summarized at each scheduled time point. The percentage of subjects with QTc interval >450 milliseconds, >480 milliseconds, or >500 milliseconds will be summarized, as will the percentage of subjects with QTc interval increases from baseline >30 milliseconds or >60 milliseconds.

All clinically relevant abnormalities in ECG waveform that are changes from the baseline readings will be reported (eg, changes in T-wave morphology or the occurrence of U-waves).

Vital Signs

Descriptive statistics of temperature, heart rate, pulse oximetry, respiratory rate, and blood pressure (systolic and diastolic) (supine) values and changes from baseline will be summarized at each scheduled time point. The percentage of subjects with values beyond clinically important limits will be summarized.

Physical Examination

Results of physical examinations (abnormalities) will be listed.

C-SSRS

Suicide-related thoughts and behaviors based on the C-SSRS will be summarized by treatment group in incidence and shift tables. Separate endpoints for suicidal ideation and suicidal behavior will be defined and summarized descriptively by treatment group. Missing scores will not be imputed.

PWC-20, CADSS, CGADR, MOAA/S, BPRS+, and POMS-2

Physician Withdrawal Checklist; 20-item (PWC-20) rating scale, dissociative data from the CADSS, alertness data from the CGADR, sedation data from the MOAA/S, psychosislike effect data from the BPRS+ and abuse-liability data from POMS-2 will be summarized descriptively at each scheduled visit by treatment group.

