| Parameter | Analysis Phase | Scheduled Day ^a | Time Interval (label on output) | Time Interval ^a (Day) | Target Time Point ^a (Day) | |
|-----------|--------------------|----------------------------|---------------------------------|----------------------------------|--------------------------------------|----|
| | | OL 8 | Day 8 (OL) | 2-11 | 8 | |
| | | OL 15 | Day 15 (OL) | 12-18 | 15 | |
| | | OL 22 | Day 22 (OL) | 19-25 | 22 | |
| | | OL 28 | Day 28 (OL) | 26 to end of OL | 28 | |
| | | OL final visit | End Point (OL) | 2 to end of OL | | |
| | OL FU | OL F/U 7 | Week 1 (OL F/U) | OL FU start day-10 | 7 | |
| | | OL F/U 14 | Week 2 (OL F/U) | 11-21 | 14 | |
| | | OL F/U 28 | Week 4 (OL F/U) | 22 to end of OL F/U | 28 | |
| | | OL F/U final visit | End Point (OL F/U) | 1 to end of OL F/U | | |
| POMS-2 | DB | 25 | Day 25 (DB) | 2 to end of DB | 25 | |
| | DB FU | DB F/U 7 | Week 1 (DB F/U) | DB F/U start day-10 | 7 | |
| | | DB F/U 14 | Week 2 (DB F/U) | 11-21 | 14 | |
| | | DB F/U 28 | Week 4 (DB F/U) | 22 to end of DB F/U | 28 | |
| | | DB F/U final visit | End Point (DB F/U) | 1 to end of DB F/U | | |
| | PT | 32 | Week 1 (PT) | PT start day to 35 | 32 | |
| | | 39 | Week 2 (PT) | 36-46 | 39 | |
| | | 53 | Week 4 (PT) | 47-60 | 53 | |
| | | 67 | Week 6 (PT) | 61-74 | 67 | |
| | | 81 | Week 8 (PT) | 75-95 | 81 | |
| | | 109 | Week 12 (PT) | 96-123 | 109 | |
| | | 137 | Week 16 (PT) | 124-151 | 137 | |
| | | 165 | Week 20 (PT) | 152-179 | 165 | |
| | OL FU | OL F/U 7 | Week 1 (OL F/U) | OL FU start day-10 | 7 | |
| | | OL F/U 14 | Week 2 (OL F/U) | 11-21 | 14 | |
| | | OL F/U 28 | Week 4 (OL F/U) | 22 to end of OL F/U | 28 | |
| | | OL F/U final visit | End Point (OL F/U) | 1 to end of OL F/U | | |
| | SDS | DB | 1 | Baseline (DB) | ≤1 (predose) | 1 |
| | | | 28 | Day 28 (DB) | 2 to end of DB | 28 |
| PT | | 39 | Week 2 (PT) | PT start day to 46 | 39 | |
| | | 53 | Week 4 (PT) | 47-60 | 53 | |
| | | 67 | Week 6 (PT) | 61-74 | 67 | |
| | | 81 | Week 8 (PT) | 75-95 | 81 | |
| | | 109 | Week 12 (PT) | 96-123 | 109 | |
| | | 137 | Week 16 (PT) | 124-151 | 137 | |
| | | 165 | Week 20 (PT) | 152-179 | 165 | |
| | | 193 | Week 24 (PT) | 180 to end of PT | 193 | |
| CGI-S | Screening /lead-in | | Week -6 (SL) | | | |
| | | | Week -4 (SL) | | | |
| | | | Week -2 (SL) | | | |
| | DB | 1 | Baseline (DB) | ≤1 (predose) | 1 | |
| | | 8 | Day 8 (DB) | 2-11 | 8 | |
| | | 15 | Day 15 (DB) | 12-18 | 15 | |
| | | 22 | Day 22 (DB) | 19-25 | 22 | |

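### SAP 5.5.7 leaves out the end-of-double-blind POMS-2, which Protocol 11.8 promises to summarise by treatment group, and the scale's visit day and baseline are unsettled

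*SAP*

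**What the plan says.** Protocol 9.6 gives the scale's purpose: "The POMS-2 will be used to measure the abuse-liability of intranasal esketamine administered twice a week for 4 weeks", at time points in Schedules 1 and 2. In Schedule 1 the only POMS-2 marks are at Visit 3.10 (Day 28) and EW. Schedule 2 continues it into the posttreatment (PT) and follow-up phases. Schedule 3 (open-label induction) has no POMS-2 row. Protocol 11.8 commits that "abuse-liability data from POMS-2 will be summarized descriptively at each scheduled visit by treatment group".

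SAP Table 1 sets up one double-blind analysis visit for the scale: "POMS-2 | DB | 25 | Day 25 (DB) | 2 to end of DB | 25". It has no baseline row for POMS-2.

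SAP 5.5.7 is the only place where POMS-2 output is specified. Scores and changes from baseline are to be summarised by time point "during PT phase and follow-up phases. Mean (SE) POMS-2 values, total scores and each component scores, will be presented graphically" for the same phases. The double-blind induction phase is not named. The neighbouring SAP 5.5.6 does report PWC-20 at the end of induction and names that assessment as the baseline before treatment stops.

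**The concern.** The protocol uses POMS-2 to measure the abuse liability of a four-week course of dosing. If the SAP is followed as written, the one POMS-2 that looks back mainly on that course is collected and windowed but gets no table or figure.

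The randomised comparison also goes. After Day 28 responders enter the PT phase, and the follow-up set FU (DB) in SAP 2.4.4 is defined as nonresponders. Every planned POMS-2 summary is therefore conditional on MADRS response, a post-randomisation outcome closely tied to a mood scale that contains depression, fatigue and vigor components.

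**Working it through.** The plan gives no figure to reproduce, so the check is day arithmetic plus a comparison of sections.

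**Inputs**
- Dosing: "treatment sessions occurring twice a week for 4 weeks at the clinical site under clinical supervision" (Protocol 3.1). Schedule 1 places the 8 sessions on Days 1, 4, 8, 11, 15, 18, 22 and 25.
- Recall: "The recall period for this study is 7 days" (SAP 5.5.7).
- Visit windows: Day 28 ±1, Day 32 +3, Day 39 ±3, and F7 and F14 ±3 (Schedules 1 and 2).
- Follow-up starts the day after the double-blind end date (SAP 2.1.2). If that end date is Day 28, F7 is study Day 28 + 7 = 35 and F14 is Day 42.

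**Look-back.** For an assessment on Day d, count the doses in Days d−7 to d (seven full days before) or in Days d−6 to d (assessment day counted as one of the seven).

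| POMS-2 assessment | d−7 to d | d−6 to d |
|---|---|---|
| Day 28 (Schedule 1) | Days 21–28: 22, 25 → 2 | Days 22–28: 22, 25 → 2 |
| Day 25 predose (SAP label) | Days 18–25: 18, 22 → 2 | Days 19–25: 22 → 1 |
| PT Day 32 | Days 25–32: 25 → 1 | Days 26–32: 0 (1 if the last dose was a day late) |
| PT Days 34 and 35 (late in window) | 0 | 0 |
| F7, Day 35 | Days 28–35: 0 | 0 |
| PT Day 39 (earliest 36) | Days 29–36: 0 | 0 |
| F14, Day 42 (earliest 39) | 0 | 0 |

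At Day 33 the last dose is reached only if it was given on Day 26 and the first counting rule applies. F7 done at its −3 limit (Day 32) behaves like the Day 32 row. At Day 29 the Day 28 form still covers 2 doses, or 1 under the second rule. So the Day 28 form covers 2/8 = 25% of sessions, the first PT visit at most 1/8 = 12.5%, and PT visits from Day 39 none.

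**Does Day 28 fall in the PT phase by definition?** A Schedule 1 footnote treats Visit 3.10 as the start day of the posttreatment phase. SAP 2.1.2, however, starts PT the day after the double-blind end date, and that end date is no earlier than the last double-blind visit. Under the SAP the Day 28 form therefore belongs to the double-blind row of Table 1 and lies outside the scope of 5.5.7.

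**Is a baseline available?** SAP 2.2 defines Baseline (DB) as the last assessment before the first double-blind dose, and applies it to the double-blind follow-up and PT phases. The first scheduled POMS-2 is at Day 28 or EW, so that value does not exist. The changes that 5.5.7 asks for in those two phases cannot be computed as defined.

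**The case against.** Four points on the other side have force.

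1. A reader might infer that abuse liability as a whole would be judged off drug. The SAP does not support that. SAP 5.1 has a special-interest category of adverse events suggestive of abuse potential, reported for both induction phases, and CADSS, BPRS+ and MOAA/S are summarised on dosing days. The gap is in POMS-2 scores only.
2. Protocol 3.1 and 3.2.2 place the evaluation of withdrawal symptoms and abuse liability in the first 4 weeks of the PT phase, and 3.1 names POMS-2 for it. This stands, and it rules out treating the PT and follow-up POMS-2 as data for some other purpose. It does not cancel the commitment in 11.8 or the reference to Schedule 1 in 9.6.
3. A reader might argue from plasma levels that only Day 28 reflects drug. With the half-lives of 5.86 to 9.83 h in Protocol 1.1.2.1, the fraction left 72 h after the Day 25 dose is 2^(−72/5.86) ≈ 0.02% to 2^(−72/9.83) ≈ 0.6%. Subjects are essentially drug-free at Day 28 as well, so the case rests on the recall window.
4. The end-of-double-blind value might be meant as the reference for later changes, as it is for PWC-20 in 5.5.6. That is possible, but 5.5.7 does not say so and SAP 2.2 defines baseline otherwise. Even on that reading no end-of-double-blind table by arm is specified.

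**Conclusion.** The omission is real. SAP 5.5.7 departs from Protocol 11.8 and leaves a window in SAP Table 1 unused. What is lost is one descriptive safety summary. The primary result is unaffected, and the abuse-liability assessment does not rest on POMS-2 alone.

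The omitted assessment matters because its recall covers 2 of 8 sessions, against at most 1 at the next scheduled visit, and because it precedes the split by response. This assumes that sessions fall close to schedule, the form is completed on or near Day 28, and the double-blind phase ends on Day 28.

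Two limits apply. The data cover subjects with a Day 28 or EW form, so it would be wrong to read this as all randomised subjects: those who withdraw consent have no EW visit. An EW form may also come up to a week after discontinuation and so reach fewer doses. Second, without a score before the first dose, and with a total that includes depression, fatigue and vigor, any difference between arms is mixed with the antidepressant effect.

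**What to change.** In SAP 5.5.7:
- Add a descriptive summary of end-of-double-blind POMS-2 total and component scores by randomised treatment on Safety (DB), for subjects with a Day 28 or EW assessment. Add a note that differences between arms are mixed with antidepressant effect. 90% confidence intervals are optional, since Protocol 11.8 promises description only.
- State the reference value for POMS-2 changes, for example the end-of-double-blind assessment, as 5.5.6 does for PWC-20.

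In SAP Table 1, reconcile the POMS-2 label and target of Day 25 with Schedule 1's Day 28.

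Keep the PT and follow-up summaries, and their stated purpose, as they are. The cost is about one table and two clarifying edits, from data already collected and windowed.

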6.1. Pharmacokinetics (Plasma concentrations)

6.1.1. Statistical Analysis of Pharmacokinetics: (Descriptive Statistics)

Descriptive statistics (N, mean, standard deviation, %CV, median, minimum and maximum) will be calculated to summarize plasma esketamine and noresketamine concentrations at each sampling time point by esketamine treatment and study day (Day 4[DB], Day 25[DB] and Day 25[OL]). Subjects will be excluded from the PK analysis if their data did not allow for accurate assessment (eg, incomplete administration of the study drug; missing information of dosing and sampling times).

For descriptive statistics of the plasma esketamine and noresketamine, following data handling rules will be applied:

- Data from samples outside Visit window rule and Time window rule specified in Section 2.3 Table 1 and Table 10 will be excluded in the calculation.
- BQL will be substituted with “0 (zero)”.
- Number of plasma concentration data will be calculated based on the number of subjects with measurable value including BQL.
- When more than half (>50%) of plasma concentration are BQL at each scheduled time point, mean, median, and minimum will be shown as ‘BQL’, and SD, and %CV will be shown as “NC” (not-calculated), respectively. If all plasma concentrations are BQL, maximum will also be shown as “BQL”.
- When number of plasma concentration data is equal to or less than 2, only N and mean will be calculated and SD, %CV, median, minimum and maximum will be shown as “NC” regardless of the proportion of BQL, respectively.
- If the dose level is modified from the initially planned dose on blood sampling day, plasma concentration data for that day will be excluded from the descriptive statistics.

Table 10: Pharmacokinetic sampling time per Protocol and for analysis

| | Nominal time (Analysis time point) | | Time window | |
|----------|------------------------------------|-------|-----------------|-------|
| | (h) | (min) | (min) | |
| Postdose | 0.67 | 40 | 32 | - 48 |
| | 1 | 60 | 48 ^a | - 72 |
| | 2 | 120 | 96 | - 144 |

^a: If PK sample for 40 min post dose is collected at 48 min, 48 min is not included in the time window for PK sampling at 1 h post dose.

The plasma esketamine and noresketamine concentrations will be tabulated and summarized by esketamine treatment, respectively. Individual concentrations will be listed.

Population PK analysis of plasma concentration-time data of esketamine (and noresketamine or other metabolites, if needed) will be performed with non-linear mixed-effects modeling (NONMEM) approach. If deemed necessary, data will be combined with data from other studies. Details will be given in a population PK analysis plan will be presented in a separate report

6.1.2. Generating Pharmacokinetic Profiles

The following graphs will be produced:

- Boxplot of the esketamine exposure at 40 minutes, 1 and 2 hours postdose (DB induction phase, Study Day 4 and Study Day 25).
- Boxplot of the noresketamine exposure at 40 minutes, 1 and 2 hours postdose (DB induction phase, Study Day 4 and Study Day 25).

6.2. Pharmacokinetic/Pharmacodynamic Relationships

The PK/PD analysis will be based on the PK/PD analysis set (defined in Section 2.4.6) for nominal time-matched plasma concentrations and safety parameters.

Safety parameter: blood pressure (DBP and SBP), QTcF and CADSS total score

- DBP and SBP: 40 minutes and 1 hour postdose, Day 4(DB), 25(DB) and Day 25(OL)
- QTcF: 1 hour postdose, Day 25(DB) and Day 25(OL)
- CADSS total score: 40 minutes, Day 4(DB), 25(DB) and Day 25(OL)

The following plots will be generated to evaluate the relationship between safety parameter (absolute value and change [change from predose for SBP, DBP and CADSS total score, change from baseline for QTcF]) and plasma concentrations of esketamine by phases:

- DBP at each time-matched point of measurement from each dose will be plotted against the corresponding plasma concentration of esketamine.
- SBP at each time-matched point of measurement from each dose will be plotted against the corresponding plasma concentration of esketamine.
- QTcF at each time-matched point of measurement from each dose will be plotted against the corresponding plasma concentration of esketamine.

- CADSS total score at each time-matched point of measurement from each dose will be plotted against the corresponding plasma concentration of esketamine.
- Additional plots will be produced, if deemed necessary.

Pearson product moment correlations (R^2) will be calculated for nominal time-matched plasma concentrations and safety parameter.

The above analyses will be repeated for noresketamine.

Population PK/PD (MADRS total score and possibly selected AEs as additional PD parameters) analysis may be evaluated. If there is any visual trend in graphical analysis, suitable models will be applied to describe the PK/PD relationships. Details will be given in a PK/PD analysis plan will be presented in a separate report.

REFERENCES

| Gamma glutamyl transferase [U/L] | N/A | 300 |
| Glucose [mmol/L] | 2.2 | 16.7 |
| Phosphate [mmol/L] | 0.7 | 2.6 |
| Potassium [mmol/L] | 3.0 | 5.8 |
| Sodium [mmol/L] | 125 | 155 |
| Bilirubin, total [μ mol/L] | N/A | 51.3 |
| Protein, total [g/L] | 50 | N/A |
| Urine pH | N/A | 8.0 |
| Hematocrit [fraction] - female | 0.28 | 0.5 |
| - male | 0.24 | 0.55 |
| Hemoglobin [g/L] | 80 | 190 |
| Neutrophils, segmented [%] | 30 | 90 |
| Monocytes [%] | N/A | 20 |
| Eosinophils [%] | N/A | 10 |
| Basophils [%] | N/A | 6 |
| Lymphocytes [%] | 10 | 60 |
| Platelet count [$\times 10^9$ /L] | 100 | 600 |
| Red blood cell count [$\times 10^{12}$ /L] -- female | 3.0 | 5.5 |
| -- male | 3.0 | 6.4 |
| White blood cell count [$\times 10^9$ /L] | 2.5 | 15.0 |
| Hy's Law criteria: | | |
| Alanine transaminase (SGPT) [U/L] | | > 3X ULN |
| AND | | |
| Bilirubin, total [μ mol/L] | | >2X ULN |

Note: The same limits apply to both males and females unless sex is indicated; N/A = Not applicable.
